***In vitro* experiments on human biological material (according to GLP, GCP):**

Isolation and cultivation of macrophages. Macrophages will be isolated from biological material (blood) or derived from blood monocytes. Macrophages will be resuspended in RPMI-1640 nutritional medium. Then the concentration of cells in RPMI 1640 will be adjusted to reflect a concentration of 1×10^6 /ml. [11]. After macrophage isolation the degree of macrophage survival should not be less than 95% (standard technique with trypan blue). The cell suspension will be distributed in a 48-well plate, with each well containing an expected 0.5×10^6 cells per well containing 0.5 ml of RPMI 1640 medium. Macrophage cultivation will be carried out at 37°C and 5% CO₂.

Determination of macrophage phenotype will be performed using the same methods as for animal biological materials.

Macrophage plasticity will be defined by standard criteria similar to macrophage phenotype detection. We will use the definition of morphological phenotype (ordinary light microscope with magnification power 15x40), receptor phenotype (percentage of expression of superficial and cellular receptors - CD80 for M1 phenotype and CD206 for M2 phenotype [12, 13], in the isolated macrophages during flow cytometry by means of CD80 and CD206 monoclonal antibodies [Beckman Coulter, USA; BD Pharmingen, USA].) and functional phenotype (NO and cytokine (pro-inflammatory, such as IL-12 (M1 markers) and anti-inflammatory, such as IL-10 (M2 markers)) production [22]. After determining the macrophage phenotype (see «Determination of macrophage phenotype»), the phenotypic plasticity (PhP) will be calculated. PhP of M1 will be calculated as percent change in the M1/M2 ratio under the action of M1 reprogramming factors and PhP of M2 will be calculated as percent change in the M2/M1 ratio under the action of M2 reprogramming factors. The phenotype marker ratio in standard culture conditions (10% FBS) will be taken as 100%.

7.0 SAFETY

There will be no investigational product in the study.

It is planned to assign the standard treatment for GERD and complications thereof (Barrett's oesophagus) on the measurement results of 24-h esophageal pH-impedance test - on the next day after visit #5.

However some medication may be prescribed before the study completion in case of need and in the interest of patient. In case any Abbott product will be part of the patient's treatment regime any safety issue or safety signal, which would negatively impact the benefit-risk ratio of the concerned Abbott product and that is detected during conduct of the study is to be reported promptly to the Affiliate safety representative.

8.0 ETHICS AND QUALITY

The study will be conducted in accordance with protocol and all applicable regulatory requirements: ICH Guideline for Good Clinical Practice (GCP), guiding principles of the Declaration of Helsinki, guiding principles of Good Laboratory Practice (GLP), International Guiding Principles for Biomedical Research Involving Animal and all applicable local regulations.

Patient's written authorization for use and/or disclose personal and/or health data must be obtained prior to enrolling each patient in the program and patients not willing to provide such written authorization will not be included in the program. However, all reasonable efforts will be made in order to avoid subject identifying information (such as name, address, etc.).

The protocol and relevant program documents will be submitted for review and approval of Regulatory Authorities (if applicable) and Local Ethics Committee(s) (LECs) and the study will start only after obtaining written approval from the Regulatory Authorities (if applicable) and LECs of both Institutions.

All data will be captured and handled in such a way so as to not reveal identity of individual patients and hence patient confidentiality will be maintained at all times.

The physician/investigator will be responsible for ensuring that a quality control and quality assurance system is in place to ensure that the program is conducted and data generated, documented, and reported in compliance with the protocol, accepted standards of Good Clinical Practice, and any applicable local laws and regulations. The investigators shall be solely responsible for regulatory and legal compliance.

The animal part of the study will be conducted in accordance with all applicable regulatory requirements: International Guiding Principles for Biomedical Research Involving Animal, APS's Guiding Principles in the Care and Use of Vertebrate Animals in Research and Training, GLP (as described above).

9.0 STATISTICAL METHODS

This is an experimental, interventional, non-randomized study. The primary purpose of the this study is exploratory in its general sense and no hypothesis is being tested, therefore no sample size calculation was performed.

Planned enrollment in this study constitutes 90 patients in clinical part and 90 subjects (mice) in animal (in vitro) part.

Statistical analysis will be performed using the STATISTICA 8.0 software for Windows (StatSoft Inc, the USA).

Normality of data distribution will be tested by using either the Shapiro-Wilk or Kolmogorov-Smirnov test.

In case of normal (Gaussian) distribution of data significance of differences will be determined by Student's t-test. In cases with non-normal distribution we will use non-parametrical U-test according to the method of Mann-Whitney for independent samples.

Tests resulting in p-values less than or equal to 0.05 will be reported as "statistically significant».

Continuous data will be summarized using descriptive statistics, and the following parameters will be reported: number of observations (n), mean and standard deviation (SD); minimum (Min), and maximum (Max); median. 95 % CI will be calculated.

Categorical data will be presented using frequency (n) and percentage (%).

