6.2. Number of subjects to be enrolled

Animal (in vitro) Part of the study:

M1 macrophages from mice of genetic line C57/BL6 (90±15 mice) – 90±15 samples
i.e. number of laboratory sockets: 180±30 (90±15 samples in double)

Clinical (patients) Part of the study:

30±5 patients with non-erosive GERD (NERD, as confirmed by endoscopy)

30±5 patients with erosive GERD

30±5 patients with Barrett's oesophagus

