6.6. Description of Activities

Visit 1 (Baseline, Day 0)

The procedures of visit:

- **Signed informed consent**

Patients considered eligible will be informed about the general aspects and procedures of the study and have to sign informed consent prior to any assessment or procedure is conducted.

- **Assignment of patient identification number**

Each patient will be assigned a two-digit patient identification number (ascending from 01 to 90).

- **Inclusion / exclusion criteria assessment**

The following criteria should be checked prior to study enrollment:

Inclusion criteria:

1. Signed informed consent
2. Gender: Male or female
3. Age: 18-65 years of age
3. Clinically and/or endoscopically confirmed diagnosis of GERD

Exclusion criteria

1. Current treatment or treatment with PPIs and/or H2RA 1 week prior inclusion
2. Female patients who are pregnant, planning to become pregnant or lactating
3. Any acute diseases or conditions, exacerbations of concomitant chronic diseases (including but not limited to inflammatory bowel disease (IBD), ulcer disease etc.) at study-start/ inclusion and/or which are not resolved 14 days prior to enrolment in the study.
4. Participation in a clinical trial in the past 3 months

5. Any condition which, in the opinion of investigator, makes the patient unsuitable for participation in the study

- **Demographics**

Includes information about date of birth, gender, race.

- **Medical history**

Medical history includes full medical information regarding GERD (duration of symptoms, results of previous examinations (upper gastrointestinal endoscopy, 24-h oesophageal pH-impedance or pH test, esophageal high-resolution manometry), previous and current treatment, comorbidities and concomitant medication, family history of the disease. Historic reports of undesirable events associated with past medications will be considered medical history.

- **Physical examination**

Includes the measurement of height, weight, blood pressure, pulse.

- **FSSG assessment**

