The refluxate samples required for the animal (in vitro) part of the study, will be placed into pure plastic test tubes and be stored at temperature +2-4 C until transportation to the Cellular Biotechnology of Moscow State University of Medicine and Dentistry. Transportation should be done at the temperature +2-4 C and be done within two hours after obtaining the refluxate.

- **Allocation to the subgroups of GERD**

Diagnosis of GERD (non-erosive and erosive) is made based on clinical symptoms (complaints of heartburn, regurgitation, belching, (non-cardiac) chest pain) and/or the results of an upper gastrointestinal endoscopy. Endoscopy should not have been done more than a month before inclusion. Diagnosis of Barrett's esophagus has to be endoscopically confirmed (incl. biopsy) and should not be older than 6 months prior to study enrolment.

Patients included into the study with a GERD diagnosis based on symptoms only and/or with an endoscopy performed more than one month ago prior to inclusion will be allocated to the subgroups on the result of endoscopy conducted at Visit 3.

- **Safety Assessments**

Information regarding complications of the procedure and patient complaints are to be collected and registered. After the procedure each patient will be placed under medical observation for at least for two hours. Any AEs related to the invasive study procedures, will be collected.

Only undesirable effects that are deemed at least possibly related to an Abbott medication by the investigator will be forwarded to Abbott affiliate PV

Visit 4

- **Physical examination**

Includes the measurement of blood pressure, pulse.

- **24-h esophageal pH-impedance test with esophageal high-resolution manometry**

To investigate number of reflux episodes and determine the type of refluxate (gastric, biliary, duodenogastric/mixed) in patients with different forms of acid reflux disease and complications thereof (Barrett's esophagus) pH-impedance test with esophageal high-resolution manometry (HRM) will be done.

Calibration of device by means of two standard buffer solutions at temperature 37 C is necessary before the 24-hr esophageal pH-impedance test is performed.

Procedure of pH impedance includes intranasal introduction of a probe into oesophagus and connection of the probe with the recording device and 24-hour wearing of the probe. Installation of the probe is carried out on an empty stomach.

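### Disease groups defined by diagnosis are compared only with unadjusted tests, although age, sex, height and weight are recorded, so a demographic difference can pass as a difference in macrophage phenotype or FSSG score.

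*Combined protocol and SAP*

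**What the plan says.** Section 9.0 of the combined protocol and SAP states "This is an experimental, interventional, non-randomized study". Section 6.2 sets a target for each diagnosis, for example "30±5 patients with non-erosive GERD (NERD, as confirmed by endoscopy"), with the same number for erosive GERD and for Barrett's oesophagus. Under Visit 3, Section 6.6 says that patients who enter on symptoms alone, or with an endoscopy more than a month old, "will be allocated to the subgroups on the result of endoscopy conducted at Visit 3". No section describes matching or stratification of the groups. Eligibility covers both sexes and ages 18 to 65 (Section 6.1.1).

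For differences, Section 9.0 offers two methods. The first is "In case of normal (Gaussian) distribution of data significance of differences will be determined by" Student's t-test. The second, for non-normal data, is "we will use non-parametrical U-test according to the method of Mann-Whitney for independent samples". It continues: "Tests resulting in p-values less than or equal to 0.05 will be reported as" statistically significant. It also describes the study as exploratory, with no hypothesis tested and no sample size calculation.

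At Visit 1 (Section 6.6) the demographics item "Includes information about date of birth, gender, race", and the physical examination "Includes the measurement of height, weight, blood pressure, pulse". BMI is not named but follows from height and weight. Section 9.0 gives none of these variables a place in a group comparison.

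**The concern.** Clinical primary endpoints 1 and 3 in Section 5.2 set out macrophage phenotype and mean FSSG scores by disease group. Section 9.0 does not list the contrasts to be tested, but its two-sample tests are the only tools offered for them. Neither test accepts a covariate.

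Nothing in the design makes the three groups alike in age, sex or body size. If they differ on one of these, and it is also related to the outcome, the unadjusted contrast carries that relation. The mean difference and its 95% CI shift by the same amount, and the chance of p at or below 0.05 rises above 5% even when the disease groups do not differ at equal age, sex and body size. A reader of a result labelled significant could not tell the two explanations apart.

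The point concerns the clinical part only. The mice are one strain and all male (Section 6.1.1).

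**Working it through.** **The plan's own figure.** The only figure to reproduce is enrolment: 3 × 30 = 90, which agrees with Section 9.0. The ±5 per group gives a total of 75 to 105. There is no power calculation to check.

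**Inputs from the documents.** n = 30 per group (25 to 35), Section 6.2; significance level 0.05, Section 9.0. Sidedness is not stated, so two-sided is assumed.

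**Inputs assumed.** The documents give neither a covariate gap between groups nor a covariate-outcome correlation. The range taken is a gap g of 0 to 1.0 within-group SD and a within-group correlation r of 0.2 to 0.5.

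**Formula.** With no true group effect, the bias in outcome SD units is d = g × r. The standard error of the difference is se = √(2/n) = √(2/30) = 0.258. The rejection rate of the unadjusted two-sided test, by normal approximation, is

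1 − Φ(1.96 − d/se) + Φ(−1.96 − d/se).

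**Worked case.** For g = 0.5 and r = 0.3, d = 0.15 and d/se = 0.15/0.258 = 0.58. The rate is 1 − Φ(1.38) + Φ(−2.54), about 0.089.

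**Results at n = 30 per group, per pairwise comparison:**

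| Gap (SD) | r = 0.2 | r = 0.3 | r = 0.5 |
|---|---|---|---|
| 0 | 5.0% | 5.0% | 5.0% |
| 0.25 | 5.4% | 6.0% | 7.7% |
| 0.5 | 6.7% | 8.9% | 16.2% |
| 0.8 | 9.5% | 15.3% | 34.1% |
| 1.0 | 12.1% | 21.3% | 49.1% |

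The permitted group sizes matter less than the assumptions. With a 0.8 SD gap and r = 0.3, the rate is 13.6% at n = 25 and 17.1% at n = 35.

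**Simulation at n = 30 per group**, to see whether the non-parametric branch protects and what a covariate model does (20,000 runs for the t-test and the model, 4,000 for Mann-Whitney):

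| Gap, r | t-test | Mann-Whitney | Group + covariate model |
|---|---|---|---|
| 0, 0.3 | 5.0% | 4.7% | 5.0% |
| 0.5, 0.3 | 8.8% | 7.9% | 5.2% |
| 0.8, 0.3 | 15.2% | 15.3% | 4.9% |
| 0.8, 0.5 | 33.6% | 30.9% | 5.1% |
| 1.0, 0.5 | 47.8% | 45.9% | 4.8% |

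The Mann-Whitney test is about as exposed as the t-test. The adjusted model holds 5% here because the simulation has one covariate, measured without error and linearly related to the outcome.

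**The case against.** The strongest reply is that the study is exploratory, tests no hypothesis and words its clinical endpoints descriptively, so unadjusted contrasts are enough. This lowers the stakes but does not remove the point. Section 9.0 still attaches a significance label at 0.05, and a shifted estimate and CI are shifted whatever the study is called.

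A second reply is that the harm is hypothetical. This stands. A reader might infer that the groups will differ in age, sex or body size and that the planned results will therefore be confounded. The documents do not show this: they give no group profile and no relation between these variables and phenotype or FSSG score. With no gap the rate stays at 5%.

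A third reply concerns the choice of covariates. Section 4.0 hypothesises that refluxate shapes macrophage phenotype and, through it, the type of disease, so disease form is not simply an exposure whose effect is to be isolated. BMI may lie upstream of reflux itself, so whether to adjust for it is debatable. This stands too, and is why BMI belongs in a second version of the model.

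It would also be too strong to say that the recorded variables are used nowhere. Section 9.0's general rules for summarising continuous and categorical data could cover them, although a table by disease group is not explicitly promised. Nor are the groups self-selected: diagnosis or endoscopy defines them.

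**Conclusion.** The point holds in a conditional form. It is certain from the text that the groups are not randomised, that no adjustment, matching or stratification is planned, and that suitable covariates are already recorded. The size of the harm is not known. Under the assumed correlations of 0.2 to 0.5 and 30 patients per group, the error rate per comparison runs from 5% (no gap) to 49% (1 SD gap, correlation 0.5).

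Two stronger readings are not supported. One is that demographic differences will produce false findings; the documents allow only that they can. The other is that adjustment would let the study attribute phenotype to disease form. Unmeasured confounding would remain, and the simulated return to 5% shows only that the model works when its own assumptions are true. The change is worth making because it is cheap and keeps everything already planned, but it is not a condition for the study's validity.

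**What to change.** In Section 9.0, for the clinical part:

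- Tabulate age, sex and BMI (derived from the Visit 1 height and weight) by disease group.
- For each continuous clinical endpoint, add a linear model with disease group, age and sex, and a second version that also includes BMI. Analyse phenotype ratios on the log scale; FSSG scores can be used as they are.
- Report the adjusted group differences with 95% CIs beside the unadjusted results, and describe them as associations.
- State that the endpoint counting patients by type of refluxate is categorical and lies outside this linear model.

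The cost is plan wording and minor programming, with no new visits or data. Age and sex use two degrees of freedom beyond the two group terms, and BMI one more. With 90 patients this leaves 90 − 5 = 85 residual degrees of freedom, or 84 with BMI.

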4.0 RATIONALE

According to the published data, type of esophageal injury and its mucosal response greatly depends on the nature/type of refluxate (gastric, biliary or duodenogastric/mixed) and patient immune profiles [6]. It has been shown that Th-2-predominant cytokine response leads to Barrett's esophagus. Also it was shown that acid suppression and alkaline duodenal reflux may increase the risk of Barrett's esophagus [23].

We hypothesize that the different types of refluxate may somehow differentiate macrophage phenotype and thereby the immune profile, determining the type of GERD disease and its progression.

This study is proposed to evaluate the role of motoric dysfunctions and burden of different kinds of refluxate on immune cells and the subsequent course of the disease. This study also aims to establish a bridge between instrumental findings (pH-impedance test) and clinical assessments (FSSG questionnaire), aiming to facilitate the use of simple questionnaire techniques in the clinical setting in the future.

This study will potentially also provide further insight and input into future uses and indications for prokinetics in GERD and may aid in improving the treatment concepts of GERD and complications thereof (Barrett's oesophagus).

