5.0 PROGRAM OBJECTIVE(S)

5. 1. Study Objectives:

Animal (*in vitro*)-part of the study:

1. To determine changes of macrophage phenotype and macrophage plasticity in mice, particularly C57/BL6 genetic strain after exposure to gastric refluxate (human origin)
2. To determine changes of macrophage phenotype and macrophage plasticity in mice, particularly C57/BL6 genetic strain after exposure to biliary refluxate (human origin)

3. To determine changes of macrophage phenotype and macrophage plasticity in mice, particularly C57/BL6 genetic strain after exposure to duodenogastric/mixed refluxate (human origin).

Clinical (patients) part of the study

1. To investigate blood and biopsy-origin monocyte/macrophage phenotype in patients with different forms of acid reflux disease (non-erosive GERD (NERD), erosive GERD and complications thereof: Barrett's esophagus)
2. To investigate types of refluxate (gastric, biliary, duodenogastric/mixed) in patients with different forms of acid reflux disease (non-erosive GERD (NERD), erosive GERD and complications thereof: Barrett's esophagus)
3. To investigate the relationship between clinical assessments (FSSG questionnaire) and measurements obtained from esophageal pH-impedance monitoring and esophageal high-resolution manometry.

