5.2. Primary Endpoint

Animal (*in vitro*) part of the study:

To determine changes in macrophagal phenotype from baseline after exposure to three different forms of refluxate (gastric, biliary duodenogastric/mixed) by means of assessing:

- a) Morphological characteristics (quantity of M1 (round forms) and M2 (fibroblasts-like) macrophages on 100 analyzing cells in 5 non-interfering sights).
- b) Macrophagal phagocytosis activity (mean percentage of phagocytizing cells in all peritoneal macrophagal cells and mean number of bacteria ingested by macrophages)
- c) Secretory activity (ratio of proinflammatory M1 cytokines IL-1 β , IL-8, IL-12p70, IFN γ , TNF α and TNF β to anti-inflammatory M2 cytokines IL-4, IL-5 и IL-10, as well as M1/M2 cytokines IL-2 и IL-6).

- d) Receptor characteristics (ratio of superficial markers CD80 and CD 25 (M1-markers) and CD206 and CD163 (M2-markers). Changes in M1 and M2 ratios determined on the base of receptors will also be analyzed.

Clinical (patients) part of the study:

- 1. Characteristics of blood and biopsy-origin monocyte/macrophage phenotype (morphology, receptor characteristics) in patients with different types of acid reflux disease (NERD, erosive GERD) and complications thereof: Barrett's esophagus).
- 2. Number of patients with gastric, biliary, duodenogastric/mixed refluxate within each of the different patient groups (NERD, erosive GERD and complications thereof: Barrett's esophagus).
- 3. Mean FSSG scores (acid reflux related symptoms, dysmotility symptoms) in patients with gastric, duodenogastric/mixed reflux related to the three different patient subgroups (NERD, erosive GERD and complications thereof: Barrett's esophagus).

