6.1.1 Inclusion Criteria

Animal (in vitro) Part of study:

Mice of genetic lines C57/BL6 (black) with mean weight 24 g, mean age 10 weeks, males

Clinical (patients) part of study:

1. Signed informed consent
2. Gender: Male or Female
3. Age: 18-65 years of age
3. Clinically and/or endoscopically confirmed diagnosis of GERD

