6.5. Program Conduct

[figure not shown]
This is a prospective, experimental study consisting of the two parts: a clinical (patients) part and an animal (in vitro) part.

The clinical (patients) part of the study will be conducted at the Propaedeutic Clinic of Internal medicine, Gastroenterology, Hepatology of First MGMU n.a. IM Sechenov.

The animal part of the study (in vitro) will be conducted at the Moscow State University of Medicine and Dentistry.

The in vitro part of the study will be conducted in M1 macrophages from mice of genetic line C57/BL6 (90 ± 15 mice). To mirror the design of clinical part of the study and to ensure compliance with the enrolled patients' number macrophages from 30 ± 5 mice will be exposed to acid refluxate, macrophages from another 30 ± 5 mice – to biliary refluxate and from the other 30 ± 5 mice – to mixed refluxate.

Figure 1. Study design

	Visit 1	Visit 2	Visit 3	Visit 4	Visit 5
Timelines and Allowance Window	Day 1 Baseline	Day 2 (±1Day)	Day 3 (±2 Days)	Day 4 (±2 Days)	Day 5
Signed informed consent	X				
Assignment of patient identification number	X				
Inclusion and exclusion criteria assessment	X				
Allocation to the subgroups of GERD			X		
Demographics (date of birth, gender, race)	X				
Medical history	X				
Physical examination	X	X	X	X	X
FSSG assessment	X				
Blood sampling (macrophages)		X			
Hematology (RW, HIV, HbsAg, HCV)		X			
Upper gastrointestinal endoscopy with biopsy and collection of refluxate			X		
24-h esophageal pH-impedance test with esophageal high-resolution manometry				X	
Safety assessments*	X	X	X	X	X

* Any safety issues related to the invasive study procedures

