The functional macrophage phenotype was estimated by cytokine (pro-inflammatory, such as IL-12 (M1 markers) and anti-inflammatory, such as IL-10 (M2 markers)) production [22]. Cytokine concentrations will be defined by flow cytometry [Beckman Coulter FC500, USA] with multiplex definition kits. The functional phenotype of macrophage population will be estimated as a ratio of functional markers of M1 and M2 phenotypes.

Determination of macrophage phenotype after exposure to human acid refluclate, human biliary refluclate and mixed human refluclate will be performed by the above mentioned methods (the part of "Determination of macrophage phenotype") and the changes vs initial results will be registered.

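### Section 9 gives non-normal data only an independent-samples test, which does not fit the animal primary endpoint of change from baseline within each refluxate

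*Combined protocol and SAP*

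**What the plan says.** Section 5.2 sets the animal primary endpoint: "To determine changes in macrophagal phenotype from baseline after exposure to three different forms of refluxate". Section 5.1 has one animal objective per refluxate (gastric, biliary, mixed), each worded as a change after exposure. Section 6.6, on animal material, adds that "the changes vs initial results will be registered".

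Section 6.5 allocates the mice: "macrophages from 30 ± 5 mice will be exposed to acid refluxate", with two further sets of the same size for biliary and mixed refluxate. Section 6.2 plans two wells per sample but does not say what each holds.

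Section 9.0 is one short set of rules for both the clinical and the animal part. Normally distributed data get Student's t-test, with no statement of paired or unpaired form. For the rest: "In cases with non-normal distribution we will use non-parametrical U-test according to the method of Mann-Whitney for independent samples". A 95% CI is promised without a method, and p-values of 0.05 or less are to be reported as significant. The section describes the study as exploratory, with no hypothesis test and no sample size calculation.

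**The concern.** The objectives and primary endpoint ask a before-and-after question inside each refluxate group. The only test named for non-normal data assumes that the two sets of values are unrelated. Values from one mouse's cells before and after exposure may be correlated, and a test that ignores positive correlation overstates the standard error of the change. A real change could then be reported as not significant on a primary endpoint.

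The non-normal branch is a realistic one. The morphological, receptor and functional phenotypes are all defined as M1-to-M2 ratios, and ratios are often skewed. How often that branch would be used cannot be read from the documents.

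**Working it through.** **1. Are the data paired?** Three groups of 30±5 mice make 3 × (30±5) = 90±15, which is the whole animal sample in Sections 6.1 and 6.2. No mice are left as an unexposed group. Since change is to be recorded against initial results, the natural baseline is the same mouse's cells. This is an inference; the protocol does not state it.

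**2. Which comparisons does Mann-Whitney fit?**

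| Comparison | Samples | Mann-Whitney suitable? |
|---|---|---|
| NERD, erosive GERD, Barrett's, two at a time | different patients | yes |
| Change under one refluxate against change under another | different mice | yes |
| Initial against post-exposure within a refluxate | same mice (inferred) | no |

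The third row is what Sections 5.1 and 5.2 ask for.

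**3. Size of the loss.** The plan states no power figure, so there is none to reproduce. Inputs: n = 30 per refluxate (Section 6.5) and the 0.05 threshold (Section 9.0). Assumed: two-sided testing, a shift of 0.5 SD, equal SD before and after, and within-mouse correlation r from 0 to 0.5.

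Normal approximation, with the standardised shift D = 0.5 × √(30/2) = 1.936:

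- unpaired test, true type I error: 2Φ(−1.96/√(1−r))
- unpaired test, power: Φ((D − 1.96)/√(1−r))
- paired test, power: Φ(D/√(1−r) − 1.96)

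At r = 0.5, √(1−r) = 0.707. The type I error is 2Φ(−2.772) = 0.006. Unpaired power is Φ(−0.034) = 0.49. Paired power is Φ(2.739 − 1.96) = Φ(0.779) = 0.78.

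The named rank tests were simulated directly (40,000 bivariate normal samples per setting):

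| r | Mann-Whitney type I error | Mann-Whitney power | Signed-rank power | Gain, simulated | Gain, normal approximation |
|---|---|---|---|---|---|
| 0 | 0.047 | 0.45 | 0.44 | about nil | 0 |
| 0.1 | 0.038 | 0.45 | 0.48 | 2 points | 4 points |
| 0.3 | 0.021 | 0.44 | 0.59 | 14 points | 15 points |
| 0.5 | 0.007 | 0.43 | 0.73 | 29 points | 30 points |

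Signed-rank type I error stayed at 0.046 to 0.050. At the edges of the planned group size, with r = 0.5, power is 0.35 against 0.65 (n = 25) and 0.53 against 0.80 (n = 35).

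The gain also depends on the shift. At n = 30 and r = 0.5 it is 0.12 against 0.33 for 0.3 SD, and 0.91 against 0.99 for 0.8 SD.

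**4. Confidence interval.** If the interval is built as for independent samples, its width relative to the paired interval is t(0.975, 58)/t(0.975, 29)/√(1−r). At n = 30 this is 0.98, 1.03, 1.17 and 1.38 for r = 0, 0.1, 0.3 and 0.5.

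**The case against.** The strongest reply is that Section 9.0 can be read with no wrong test in it. If the recorded variable is the change itself, the mean and 95% CI of those changes already give a paired estimate within each refluxate. Mann-Whitney would then compare changes between refluxates, which use different mice. That is the contrast in the rationale: "We hypothesize that the different types of refluxate may somehow differentiate macrophage phenotype and thereby the immune profile". The phrase about independent samples can also be read as limiting where the test applies. The t-test is unqualified, so a paired t-test is not excluded.

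Much of this stands. A reader might infer that the plan directs Mann-Whitney to before and after values; it does not. The t-test form and the CI method are unspecified, not wrong. What remains is that, under any reading, a non-normal change within a refluxate has no suitable named test, although it is the primary endpoint.

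The loss may also be small. The animals are uniform ("Mice of genetic lines C57/BL6 (black) with mean weight 24 g, mean age 10 weeks, males"), so r could be low, and the study is exploratory with no planned power to lose. That limits the harm. But the plan still reports significance at 0.05, and naming the paired test costs about one point of power at most if r is 0.

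**Conclusion.** The concern holds as a mismatch between the primary endpoint and the named non-parametric test, and it should be fixed. The consequence is lost sensitivity and, if intervals are built as independent, lost precision. It rests on three conditions: both readings come from the same mouse, the non-normal rule is applied to before and after values, and r is above 0. With 30 mice and a 0.5 SD shift, the power loss runs from nil (r = 0) to about 30 points (r = 0.5). Both r and the shift are assumptions, so these figures show direction and scale only.

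Two stronger readings are not supported. A reader might infer that ignoring the pairing creates false positives. With similar spread before and after and positive r, the error goes the other way; with a three-fold rise in SD and r = 0.1, simulated type I error was only about 0.06. A reader might also infer that the animal part has no control for time in culture. The documents do not settle this: the contents of the two wells are not stated, and the standard 10% FBS culture may be meant as the reference. That is a separate question and adds nothing to the size of this point.

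**What to change.** In Section 9.0, for the animal part:

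1. Where initial and post-exposure readings come from the same mouse, analyse the within-mouse change, with one value per mouse per state and replicate wells averaged.
2. Check normality on that change. Use a paired t-test if it is acceptable and Wilcoxon signed-rank if not, and report a 95% CI for the paired change.
3. Keep independent-samples tests for patient groups and for comparing change between refluxates.

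Separately, and not as part of this error, state in Section 6.2 what the two wells per sample hold. Also reconcile the times in Section 6.4.2, where 48 h of culture plus 24 h of assessment makes 72 h against a stated total of 36 h. If there is no concurrent unexposed reference, describe within-refluxate results as change over time, not as an effect of refluxate.

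The cost is wording only, with no extra mice, wells or assays, provided that a same-mouse initial reading is already planned. If it is not, the paired analysis does not apply, and the protocol should say what the baseline is.
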